11.2.5	Abnormal Involuntary Movement Scale (AIMS).....	21
11.2.6	Barnes Akathisia Rating Scale (Barnes).....	21
11.2.7	Massachusetts General Hospital Sexual Functioning Questionnaire (MSFQ).....	21
11.2.8	Resource Utilization Scale.....	22
12	Appendices.....	23
13	Proposed List of Summary Tables.....	26

List of In-text Tables

Table 9.4-1	Categorical Change Criteria in QT/QTc Parameters	17
Table 11.1-1	Study Day and Visit Windows.....	19

List of Appendices

Appendix 1	Criteria for Identifying Vital Signs of Potential Clinical Relevance	23
Appendix 2	Criteria for Identifying Laboratory Values of Potential Clinical Relevance	24
Appendix 3	Criteria for Identifying ECG Measurements of Potential Clinical Relevance	25

List of Abbreviations and Definition of Terms

Abbreviation	Definition
ADT	Antidepressant Therapy
AE	Adverse event
AIMS	Abnormal Involuntary Movement Scale
BARS	Barnes Akathisia Rating Scale
BMI	Body mass index
C-SSRS	Columbia-Suicide Severity Rating Scale
CRF	Case report form
ECG	Electrocardiogram
ET	Early termination
ICF	Informed consent form
IMP	Investigational medicinal product
LOCF	Last-observation-carried-forward
MedDRA	Medical Dictionary for Regulatory Activities
OC	Observed case
SAP	Statistical analysis plan
SAS	Simpson Angus Scale
TEAE	Treatment-emergent adverse event
ULN	Upper limit of normal

1 Introduction

This statistical analysis plan (SAP) documents the statistical methodology and data analysis algorithms and conventions to be applied for statistical analysis and reporting of safety and tolerability data of Study 331-10-238. All amendments to the protocol are taken into consideration in developing this SAP.

2 Trial Objectives

Primary: To assess the long-term safety and tolerability of oral brexpiprazole as adjunctive therapy in the treatment of adults with MDD.

Secondary: To assess the long-term efficacy of oral brexpiprazole as adjunctive therapy in the treatment of adult patients with MDD.

3 Trial Design

3.1 Type/Design of Study

3.1.1 Trial Design Before Protocol Amendment 3

This is a multicenter, **52-week**, open-label trial designed to assess the long-term safety, tolerability, and efficacy of adjunctive brexpiprazole in depressed adults on concurrent antidepressant therapy (ADT). The trial will be conducted on an outpatient basis.

Enrollment into the trial will be drawn from eligible subjects who have completed one of the double-blind, phase 3 brexpiprazole MDD trial and who, in the investigator's judgment, could potentially benefit from adjunctive treatment with oral brexpiprazole for MDD. A schematic of the study design is presented in [Figure 3.1-1](#).

The trial will be organized as follows:

Screening/Baseline: Subjects will be screened for eligibility at the last scheduled visit of the prior double-blind phase 3 trial. Subjects will sign a separate informed consent form (ICF) for participation in Trial 331-10-238 before any procedures specific to the open-label trial are performed. The assessments from the last scheduled visit of the prior double-blind phase 3 trial will serve as the baseline measures for Trial 331-10-238 for any assessment that is not unique to the open-label trial. Medical history will be updated, if necessary.

Treatment Phase: Eligible subjects will receive daily treatment with open-label brexpiprazole and ADT as described in the Investigational Medicinal Product (IMP), Dose, Formulation, Mode of Administration section. Visits will occur at the end of

Weeks 1, 2, 4, 8, 14, 20, 26 32, 28, 44, and 52. All subjects will receive up to 52 weeks of open-label treatment in Trial 331-10-238.

Follow-up: Subjects will be followed up for safety via telephone contact or clinic visit 30 (+ 2) days after the last dose of open-label medication.

[figure not shown]

Figure 3.1-1 Trial Design Schematic

3.1.2 Trial Design After Protocol Amendment 3

This is a multicenter, **26-week**, open-label trial designed to assess the long-term safety, tolerability, and efficacy of adjunctive brexpiprazole in depressed adults on concurrent antidepressant therapy (ADT). The trial will be conducted on an outpatient basis. Enrollment into the trial will be drawn from eligible subjects who have completed one of the double-blind, phase 3 brexpiprazole MDD trial and who, in the investigator's judgment, could potentially benefit from adjunctive treatment with oral brexpiprazole for MDD. A schematic of the study design is presented in [Figure 3.1-2](#).

The trial will be organized as follows:

Screening/Baseline: Subjects will be screened for eligibility at the last scheduled visit of the prior double-blind phase 3 trial. Subjects will sign a separate informed consent form (ICF) for participation in Trial 331-10-238 before any procedures specific to the open-label trial are performed. The assessments from the last scheduled visit of the prior double-blind phase 3 trial will serve as the baseline measures for Trial 331-10-238 for any assessment that is not unique to the open-label trial. Medical history will be updated, if necessary.

Treatment Phase: Eligible subjects will receive daily treatment with open-label brexpiprazole and ADT as described in the Investigational Medicinal Product (IMP), Dose, Formulation, Mode of Administration section. Visits will occur at the end of Weeks 1, 2, 4, 8, 14, 20, and 26. All subjects will receive up to 26 weeks of open-label treatment in Trial 331-10-238.

Follow-up: Subjects will be followed up for safety via telephone contact or clinic visit 30 (+ 2) days after the last dose of open-label medication.

[figure not shown]

Figure 3.1-2 Trial Design Schematic

3.2 Study Population

The subject population will consist of eligible subjects who, in the investigator's judgment, could potentially benefit from adjunctive treatment with brexpiprazole for MDD and who meet one of the following conditions:

- Subjects who completed participation in the Double-blind Randomization Phase (ie, Week 14 visit of Phase B) in Trial 331-10-227 or Trial 331-10-228 or
- Subjects who met criteria for a response at the end of prospective treatment (ie, Week 8 visit of Phase A) in Trial 331-10-227 or Trial 331-10-228, **BUT DID NOT** meet criteria for remission (defined as a MADRS Total Score of ≤ 10) at the Week 14 visit of Phase A+ in Trial 331-10-227 or Trial 331-10-228.

Subjects must qualify for Trial 331-10-238 at the last visit of the double-blind trial and must be able to continue therapy without interruption between the double-blind and open label trials. Based on the projected enrollment estimates for the double-blind phase 3 trials (ie, Trial 331-10-227 and Trial 331-10-228), up to 1280 subjects may enroll into Trial 331-10-238.

4 Sample Size and Power Justification

The sample size is not based on statistical power considerations. The trial population will be derived from eligible subjects from the double-blind phase 3 trials (ie, Trial 331-10-227 and Trial 331-10-228). Therefore, the number of eligible subjects will be limited by the number of subjects enrolled into these protocols. Based on the projected enrollment estimates for the double-blind phase 3 trials (ie, Trial 331-10-227 and Trial 331-10-228), up to 1280 subjects may enroll into Trial 331-10-238.

5 Statistical Methods

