Subject Population:	
The subject population will consist of eligible subjects who, in the investigator's judgment, could potentially benefit from adjunctive treatment with brexpiprazole for MDD according to the following criteria:
 
 • Subjects who participated in Trial 331-10-227, Trial 331-10-228 or 331-13-214 will be eligible for the 331-10-238 trial if they meet one of the following conditions: • Subjects who completed participation in the double-blind randomization phase (ie, Week 14 visit of Phase B) in Trial 331-10-227, Trial 331-10-228 or Trial 331-13-214 or • Subjects who continued into Phase A+ (were not randomized into Phase B) at the end of prospective treatment (ie, Week 8 visit of Phase A) in Trial 331-10-227, Trial 331-10-228 or Trial 331-13-214, BUT DID NOT meet criteria for remission (defined as a Montgomery Asberg Depression Rating Scale Total Score of ≤ 10) at the Week 14 visit of Phase A+ in Trial 331-10-227, Trial 331-10-228 or Trial 331-13-214. • Subjects who participated in another double-blind phase 3 brexpiprazole MDD trial will be eligible for 331-10-238 Trial if they have completed the last scheduled visit of the prior double-blind phase 3 trial. • Subjects must qualify for Trial 331-10-238 at the last scheduled visit of the prior double-blind phase 3 trial and

	
must be able to continue therapy without interruption between the double-blind and open label trials. Based on the projected enrollment estimates for the prior double-blind phase 3 brexpiprazole MDD trials, up to approximately 3,000 subjects may enroll into Trial 331-10-238.

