3.3 Trial Population

The trial population will consist of eligible subjects who, in the investigator's judgment, could potentially benefit from adjunctive treatment with brexpiprazole for MDD according to the following criteria:

- Subjects who participated in Trial 331-10-227, Trial 331-10-228 or Trial 331-13-214 will be eligible for Trial 331-10-238 if they meet one of the following conditions:
 - Subjects who completed participation in the double-blind randomization phase (ie, Week 14 visit of phase B) in Trial 331-10-227, Trial 331-10-228 or Trial 331-13-214 or
 - Subjects who continued into Phase A+ (were not randomized into Phase B) at the end of prospective treatment (ie, Week 8 visit of Phase A) in Trial 331-10-227, Trial 331-10-228 or Trial 331-13-214, **BUT DID NOT** meet criteria for remission (defined as a MADRS Total Score of ≤ 10) at the Week 14 visit of Phase A+ in Trial 331-10-227, Trial 331-10-228 or Trial 331-13-214.
- Subjects who participated in a double-blind phase 3 brexpiprazole MDD trial will be eligible for the 331-10-238 trial if they have completed the last scheduled visit of the double-blind phase 3 trial.
- Subjects must qualify for Trial 331-10-238 at the last scheduled visit of the prior double-blind phase 3 trial and must be able to continue therapy without interruption between the double-blind and open-label trials. Based on the projected enrollment estimates for the prior double-blind phase 3 brexpiprazole MDD trials, up to approximately 3,000 subjects may enroll into Trial 331-10-238.

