3.4.2 Inclusion Criteria

Subjects are required to meet the following inclusion criteria:

Table 3.4.2-1 Inclusion Criteria	
	All Subjects
1.	Subjects who are able to provide written informed consent and/or consent obtained from a legally acceptable representative (as required by IRB/IEC) prior to the initiation of any protocol-required procedures.
2.	Ability, in the opinion of the principal investigator, to understand the nature of the trial and follow protocol requirements, including the prescribed dosage regimens, tablet/capsule ingestion, and discontinuation of prohibited concomitant medication; to read and understand the written word in order to complete subject-reported outcomes measures; and to be reliably rated on assessment scales.
3	Male and female outpatients 18 to 65 years of age, inclusive, at the time of informed consent for Trial 331-10-238.
4	Subjects willing to discontinue all prohibited psychotropic medications starting from the time of signing the ICF and during the trial period (refer to Section 4).

Table 3.4.2-1 Inclusion Criteria	
	331-10-227, 331-10-228 and 331-13-214 Subjects Only
5.	Subjects who, in the opinion of the investigator, could potentially benefit from administration of brexpiprazole as adjunctive therapy to their antidepressant therapy and who meet one of the following criteria: a) Subjects who completed participation in the double-blind randomization phase (ie, Week 14 visit of Phase B) in Trial 331-10-227, Trial 331-10-228 or Trial 331-13-214 or b) Subjects who continued into Phase A+ (were not randomized into Phase B) at the end of prospective treatment (ie, Week 8 visit of Phase A) in Trial 331-10-227, Trial 331-10-228 or Trial 331-13-214, BUT DID NOT meet criteria for remission (defined as a MADRS Total Score of ≤ 10) at the Week 14 visit of Phase A+ in Trial 331-10-227, Trial 331-10-228 or Trial 331-10-227, Trial 331-10-228 or Trial 331-13-214...
Eligible Subjects From Other Double-Blind Phase 3 Brexpiprazole MDD Trials	
6.	Subjects who completed the last scheduled visit of the prior double-blind phase 3 trial, and who in the opinion of the investigator, could potentially benefit from administration of brexpiprazole as adjunctive therapy to their antidepressant therapy.

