7.2 Sample Size

The sample size is not based on statistical power considerations. The trial population will be derived from eligible subjects from the prior double-blind phase 3 brexpiprazole MDD

trials. Therefore, the number of eligible subjects will be limited by the number of subjects enrolled into these protocols. Based on the projected enrollment estimates for the prior double-blind phase 3 trials, up to approximately 3,000 subjects may enroll into Trial 331-10-238.

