- CT-12.1.2 Mean Change from Baseline in Electrocardiogram Results – 52-Week Enrollers
- CT-12.1.3 Mean Change from Baseline in Electrocardiogram Results – 26-Week Enrollers
- CT-12.2.1 Incidence of Potentially Clinically Relevant Changes in ECG Evaluations – All Subjects
- CT-12.2.2 Incidence of Potentially Clinically Relevant Changes in ECG Evaluations – 52-Week Enrollers
- CT-12.2.3 Incidence of Potentially Clinically Relevant Changes in ECG Evaluations – 26-Week Enrollers
- CT-12.3.1.1 Listing of Potentially Clinically Relevant Abnormalities in ECG Evaluations – All Subjects
- CT-12.3.1.2 Listing of Potentially Clinically Relevant Abnormalities in ECG Evaluations – 52-Week Enrollers
- CT-12.3.1.3 Listing of Potentially Clinically Relevant Abnormalities in ECG Evaluations – 26-Week Enrollers
- CT-12.3.2.1 Criteria for Potentially Clinically Relevant Abnormalities in ECG Evaluations
- CT-12.3.3.1 ECG Diagnosis Mapping for Potentially Clinically Relevant Electrocardiogram Abnormalities

- CT-12.4.1.1 Incidence of Categorical Changes in QT Evaluations – All Subjects
- CT-12.4.1.2 Incidence of Categorical Changes in QT Evaluations – 52-Week Enrollers

Protocol 331-10-238 Statistical Analysis Plan

- CT-12.4.1.3 Incidence of Categorical Changes in QT Evaluations – 26-Week Enrollers
- CT-12.4.2.1 Listing of Categorical Changes in QT Evaluations – All Subjects
- CT-12.4.2.2 Listing of Categorical Changes in QT Evaluations – 52-Week Enrollers
- CT-12.4.2.3 Listing of Categorical Changes in QT Evaluations – 26-Week Enrollers

Otsuka Pharmaceutical Development & Commercialization, Inc.

This page is a manifestation of an electronically captured signature

OPC-34712

SIGNATURE PAGE

Document Name: SAP 33110238_FINAL

Document Number: 0001267504

Document Version: 2.0

Signed by	Meaning of Signature	Server Date (dd-MMM-yyyy HH:mm 'GMT'Z)
[REDACTED]	Biostatistics Approval	26-May-2017 15:06 GMT+0
[REDACTED]	Clinical Approval	30-May-2017 14:21 GMT+0

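### Does the SAP's outdated enrolment ceiling of 1280, from two parent trials, call for a change to the plan?

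*SAP*

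**What the plan says.** SAP 3.2 (Study Population) and SAP 4 (Sample Size and Power Justification) give the same ceiling: "up to 1280 subjects may enroll into Trial 331-10-238". Section 4 states the source: "The trial population will be derived from eligible subjects from the double-blind phase 3 trials (ie, Trial 331-10-227 and Trial 331-10-228"). Section 3.2 restricts its two eligibility routes to the same pair of trials.

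The protocol, at Amendment 4, differs on both counts:

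- **Size.** Section 7.2 has "up to approximately 3,000 subjects may enroll into Trial 331-10-238". The Synopsis and section 3.3 give the same figure.
- **Named parent trials.** Section 3.3 has "Subjects who participated in Trial 331-10-227, Trial 331-10-228 or Trial 331-13-214 will be eligible for Trial 331-10-238", subject to conditions that follow.
- **Other parent trials.** The Synopsis adds "Subjects who participated in another double-blind phase 3 brexpiprazole MDD trial will be eligible for 331-10-238 Trial", provided they completed the last scheduled visit. The inclusion table in section 3.4.2 has a separate block headed "Eligible Subjects From Other Double-Blind Phase 3 Brexpiprazole MDD Trials".

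The SAP's introduction says "All amendments to the protocol are taken into consideration in developing this SAP". Its biostatistics approval is stamped "26-May-2017 15:06 GMT+0", almost three years after Amendment 4 of 13 June 2014.

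The two documents agree on one thing that matters here. Protocol 7.2 and SAP 4 both say that the sample size does not come from a power calculation and is limited by how many subjects the parent trials supply.

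**The concern.** A sample-size section that disagrees with the governing protocol is normally worth correcting. Here the SAP states a ceiling less than half the protocol's and omits parent trials from which the protocol allows enrolment. It does so while claiming to reflect every amendment.

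It is also hard to read the text as a deliberate record of the old design. Where the SAP means to describe a superseded design it says so: 3.1.1 is labelled as before Amendment 3 and 3.1.2 as after it. Sections 3.2 and 4 carry no such label.

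Three things could be at stake:

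- If an analysis set were tied to the stated source trials, subjects from 331-13-214 or other trials could be dropped.
- If a precision or detection claim rested on 1280, it would be wrong.
- A study report that copied these paragraphs would misdescribe the planned population.

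**Working it through.** **1. Is there a figure to reproduce?** No. Neither document gives the parent-trial enrolment or the rollover rate behind 1280 or 3,000. There is no alpha, power, effect size or margin. The check is therefore a direct comparison of current text with current text.

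| Item | SAP 3.2 and 4 | Protocol Synopsis, 3.3, 3.4.2, 7.2 |
|---|---|---|
| Ceiling | 1280 | approximately 3,000 |
| Named parent trials | 331-10-227, 331-10-228 | 331-10-227, 331-10-228, 331-13-214 |
| Other phase 3 MDD trials | not mentioned | admitted |
| Power-based | no | no |

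- Difference: 3000 − 1280 = 1,720.
- Ratio: 1280/3000 = 0.427, or 3000/1280 = 2.34 the other way. The word approximately cannot bridge that gap.

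**2. Where does 1280 come from?** The protocol's amendment summaries, used only to date the text, show that Amendment 2 (16 November 2012) replaced 1280 with 3,000 and opened entry to other phase 3 MDD trials. Amendment 3 (11 April 2014) added 331-13-214. The number and the two-trial list are thus one outdated projection, not two independent errors.

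**3. Does any analysis use it?** Take the definitions in SAP 5.1 in turn.

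- Enrolled Sample: everyone who signs the consent form for this trial.
- Safety Sample: everyone who takes at least one dose of open-label brexpiprazole with an allowed ADT.
- Efficacy Sample: members of the Safety Sample with at least one post-baseline CGI-S.

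None has a cap and none names a parent trial. A subject from 331-13-214 who consents, is dosed and is rated enters all three. SAP 8 makes efficacy descriptive. SAP 9 reports incidences and changes from baseline in the Safety Sample. Denominators are the subjects observed, or person-years observed for the resource-use rates in SAP 11.2.8. The planned ceiling enters no formula.

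**4. Could the size matter for rare adverse events?** The primary outcome is adverse events, so this is the one place where number of subjects carries information. As an illustration only, since the documents set no detection target:

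- With zero events seen, the one-sided 95% upper bound on the event rate is 1 − 0.05^(1/n). This is 0.234% at n = 1280 and 0.100% at n = 3,000.
- With an assumed true rate of 1 in 1,000, the chance of seeing at least one event is 1 − 0.999^n. This is 72% at n = 1280 and 95% at n = 3,000.

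Those differences are material, but they depend on how many subjects are actually treated. Editing the sentence in the SAP would not alter that number.

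**5. Does the SAP work for the wider population as it stands?** Yes. SAP 3.1.1 and 3.1.2 already describe the source generically, as completers of a double-blind phase 3 brexpiprazole MDD trial. SAP 5.1 summarises by parent study treatment group without limiting which parent studies count.

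**The case for a change.** The best argument for acting is that the error is certain and the correction costs almost nothing. SAP 4 is the only sample-size section in the SAP, and both facts in it are out of date. The document claims to take account of all amendments, yet it was approved 4.5 years after Amendment 2 (1,652 days from 16 November 2012 to 26 May 2017) and 3.1 years after Amendment 3 (1,141 days from 11 April 2014). All of that stands as a criticism of document control. The elapsed time does not measure any effect on the results.

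A more substantive version points to SAP 5.1: if every summary is split by parent study treatment group, the reader should know which parent trials supply the groups. This has some force. But the fix in question would only list trial numbers in a background section. It would not define the groups or say how arms from different trials combine, and analysts obtain each subject's parent trial and arm from the data in any case.

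SAP 3.2 also describes the Phase A+ route as meeting response criteria, where Protocol 3.3 speaks of continuing into Phase A+ without randomization. The protocol no longer defines response. Nothing shows that the two wordings select different subjects, and eligibility is decided at sites under the protocol, so this adds only another outdated phrase.

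What survives is the risk that a report writer copies the stale paragraph. That would misstate the plan in the report's background text while the disposition tables beside it showed the true counts and sources.

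**Conclusion.** The inconsistency is genuine: 1280 against approximately 3,000 (43%, 1,720 fewer), and two parent trials against three named ones plus others. It is a clerical slip and calls for no change to the plan. The figure is a projected rollover ceiling, not a design target. Nothing in the analysis sets, summaries or denominators draws on it, and correcting it would change neither what the trial does nor what it can conclude.

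This rests on two readings, both supported by the text: that SAP 5.1, and not the descriptive SAP 3.2, determines who is analysed; and that the protocol governs eligibility. If any output were programmed to select subjects by the two trial numbers in SAP 3.2, the conclusion would differ, but nothing in the SAP asks for that.

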5.1 Data Sets Analyzed

The following datasets are defined for this study:

- Enrolled Sample: comprises all subjects who sign an ICF for the trial.
- Safety Sample: comprises those subjects who receive at least one dose of open-label brexpiprazole as adjunctive therapy to one of the allowed ADTs.
- Efficacy Sample: comprises those subjects in the Safety Sample who have at least one post-baseline efficacy evaluation of CGI-S.

All the summaries will be done for all subjects, 52-week enrollers (before Protocol Amendment 3), and 26-week enrollers (after Protocol Amendment 3), and will be done by parent study treatment group. Selected summaries will also be done by ADT. Details of those summaries will be specified in the following sections.

The Safety Sample will be used for all baseline and safety summaries. The Efficacy Sample will be used for the efficacy summaries.

The observed case (OC) dataset will consist of the actual observations recorded at each visit and will be used to present summaries per trial week.

The last-observation-carried-forward (LOCF) data set will include data recorded at a given visit in the Treatment Phase or, if no observation is recorded at that visit, data carried forward from the previous visit in the Treatment Phase. Data collected prior to or on the first day of Treatment Phase dosing will not be carried forward or averaged with Treatment Phase data to impute missing values for the LOCF data set.

